#### Adverse Event of Special Interest (AESI)

The term AESI relates to any specific AE that has been identified at the project level as being of particular concern for safety monitoring and safety assessment within this study, e.g. the potential for AEs based on knowledge from other compounds in the same class.

The following are considered as AESIs:

No AESIs have been defined for this study.

## **11.2 ADVERSE EVENT AND SERIOUS ADVERSE EVENT COLLECTION AND REPORTING**

The investigator shall maintain and keep detailed records of all AEs in their patient files.

### Collection and reporting of AEs

The study design is of non-interventional nature and the study is conducted within the conditions of the approved marketing authorization. Sufficient data from controlled interventional trials are available to support the evidence on the safety and efficacy of the studied BI drug. For this reason the following AE collection and reporting requirements have been defined.

#### **For Objective 1**

##### Data collected on the eCRF once informed consent or waiver is obtained

- Serious and non-serious ADRs to DE from the time of VTE until the end of the study for a patient
- ALL serious and non-serious ADRs other than DE from time of informed consent/ waiver until the end of the study for a patient
- All AEs with fatal outcome

##### Data reported on the NIS AE form once informed consent or waiver is obtained

- Serious and non-serious ADRs to DE from the time of VTE until the end of the study for a patient
- All AEs with fatal outcome in patients exposed to DE

#### **For Objective 2**

##### Data collected on the eCRF once informed consent is obtained

- Serious and non-serious ADRs to DE and VKA from the time of VTE until the end of the study for a patient.

##### Data reported on the NIS AE form once informed consent is obtained

- Serious and non-serious ADRs to DE from time of VTE until the end of the study for a patient
- All AEs with fatal outcome in patients exposed to DE

All ADRs, including those persisting after study completion must be followed up until they are resolved, have been sufficiently characterized, or no further information can be obtained.

The investigator carefully assesses whether an AE constitutes an ADR using the information below.

### Causal relationship of adverse event

The definition of an adverse drug reaction implies at least a reasonable possibility of a causal relationship between a suspected medicinal product and an adverse event. An adverse drug reaction, in contrast to an adverse event, is characterized by the fact that a causal relationship between a medicinal product and an occurrence is suspected.

Medical judgment should be used to determine the relationship, considering all relevant factors, including pattern of reaction, temporal relationship, de-challenge or re-challenge, confounding factors such as concomitant medication, concomitant diseases and relevant history.

Arguments that may suggest a **reasonable causal relationship** could be:

- The event is **consistent with the known pharmacology** of the drug
- The event is known to be caused by or **attributed to the drug class**.
- A **plausible time to onset of the event** relative to the time of drug exposure.
- Evidence that the **event is reproducible** when the drug is re-introduced
- **No medically sound alternative etiologies** that could explain the event (e.g. preexisting or concomitant diseases, or co-medications).
- The event is typically **drug-related and infrequent in the general population** not exposed to drugs (e.g. Stevens-Johnson syndrome).
- An indication of dose-response (i.e. greater effect size if the dose is increased, smaller effect size if dose is diminished).

Arguments that may suggest that there is **no reasonable possibility of a causal relationship** could be:

- No plausible time to onset of the event relative to the time of drug exposure is evident (e.g. pre-treatment cases, diagnosis of cancer or chronic disease within days/weeks of drug administration; an allergic reaction weeks after discontinuation of the drug concerned)
- Continuation of the event despite the withdrawal of the medication, taking into account the pharmacological properties of the compound (e.g. after 5 half-lives).

Of note, this criterion may not be applicable to events whose time course is prolonged despite removing the original trigger.

- Additional arguments amongst those stated before, like alternative explanation (e.g. situations where other drugs or underlying diseases appear to provide a more likely explanation for the observed event than the drug concerned).
- Disappearance of the event even though the study drug treatment continues or remains unchanged.

#### Intensity of adverse event

The intensity of the AE should be judged based on the following:

- |           |                                                                            |
|-----------|----------------------------------------------------------------------------|
| Mild:     | Awareness of sign(s) or symptom(s) which is/are easily tolerated           |
| Moderate: | Enough discomfort to cause interference with usual activity                |
| Severe:   | Incapacitating or causing inability to work or to perform usual activities |

### Pregnancy

In rare cases, pregnancy might occur in a study. Once a female subject has been enrolled into the study, after having taken dabigatran etexilate, the investigator must report any drug exposure during pregnancy to the Sponsor by means of Part A of the Pregnancy Monitoring Form. The outcome of the pregnancy associated with the drug exposure during pregnancy must be followed up and reported by means of Part B of the Pregnancy Monitoring Form.

In the absence of a reportable AE, only the Pregnancy Monitoring Form must be completed, otherwise the NIS AE form is to be completed and forwarded as well within the respective timelines.

### Timelines for Expedited Reporting of AEs on the NIS AE form and Drug Exposure During Pregnancy

Type of Report	Timeline
All Serious ADRs associated with dabigatran etexilate (DE)	immediately within 24 hours
All AEs with fatal outcome in patients exposed to dabigatran etexilate (DE)	immediately within 24 hours
All non-serious ADRs associated with dabigatran etexilate (DE)	7 calendar days
All pregnancy monitoring forms	7 calendar days

The same timelines apply if follow-up information becomes available for the respective events. In specific occasions the Investigator could inform the Sponsor or the Sponsor's designee (i.e., the CRO) upfront via telephone. This does not replace the requirement to complete and fax the NIS AE form.

### Information required

For each reportable adverse event, the investigator should provide the information requested on the appropriate (e)CRF pages and the NIS AE form if applicable.

### Reporting of related Adverse Events associated with any other BI drug

The investigator is encouraged to report all adverse events related to any BI drug other than dabigatran etexilate according to the local regulatory requirements for spontaneous AE reporting at the investigator's discretion by using the locally established routes and AE report forms. The term AE includes drug exposure during pregnancy, and, regardless of whether an AE occurred or not, any abuse, off-label use, misuse, medication error, occupational exposure, lack of effect, and unexpected benefit.

## **11.3 REPORTING TO HEALTH AUTHORITIES**

Adverse event reporting to regulatory agencies will be done by the marketing authorization holder (MAH) according to local and international regulatory requirements.

## **12. PLANS FOR DISSEMINATING AND COMMUNICATING STUDY RESULTS**

Any publication must be consistent with the BI publication policy and guided by the current version of the Uniform Requirements for Manuscripts Submitted to Biomedical Journals: Writing and Editing for Biomedical Publication of the International Committee of Medical Journals.

## **ANNEX 1. LIST OF STAND-ALONE DOCUMENTS**

The stand-alone documents have not been finalized at the time of protocol finalization. The final version of these documents will be archived in the study master file.

Number	Document Reference Number	Date	Title
1			Site Management Plan
2			Data Operations Plan
3			Statistical and Epidemiological Analysis Plan
4			List of Investigators

## **ANNEX 2. ENCEPP CHECKLIST FOR STUDY PROTOCOLS**

EUROPEAN MEDICINES AGENCY  
SCIENCE MEDICINES HEALTH

European Network of Centres for  
Pharmacoepidemiology and  
Pharmacovigilance

Doc.Ref. EMEA/540136/2009

## **ENCePP Checklist for Study Protocols (Revision 2, amended)**

Adopted by the ENCePP Steering Group on 14/01/2013

The European Network of Centres for Pharmacoepidemiology and Pharmacovigilance (ENCePP) welcomes innovative designs and new methods of research. This Checklist has been developed by ENCePP to stimulate consideration of important principles when designing and writing a pharmacoepidemiological or pharmacovigilance study protocol. The Checklist is intended to promote the quality of such studies, not their uniformity. The user is also referred to the ENCePP Guide on Methodological Standards in Pharmacoepidemiology which reviews and gives direct electronic access to guidance for research in pharmacoepidemiology and pharmacovigilance.

For each question of the Checklist, the investigator should indicate whether or not it has been addressed in the study protocol. If the answer is "Yes", the page number(s) of the protocol where this issue has been discussed should be specified. It is possible that some questions do not apply to a particular study (for example in the case of an innovative study design). In this case, the answer 'N/A' (Not Applicable) can be checked and the "Comments" field included for each section should be used to explain why. The "Comments" field can also be used to elaborate on a "No" answer.

This Checklist should be included as an Annex by marketing authorisation holders when submitting the protocol of a non-interventional post-authorisation safety study (PASS) to a regulatory authority (see the Guidance on the format and content of the protocol of non-interventional post-authorisation safety studies). Note, the Checklist is a supporting document and does not replace the format of the protocol for PASS as recommended in the Guidance and Module VIII of the Good pharmacovigilance practices (GVP).

Study title: Characterization of patients following an acute venous thromboembolism (VTE) and assessment of safety and effectiveness of dabigatran etexilate (DE) in the treatment and secondary prevention of acute deep vein thrombosis (DVT) and pulmonary embolism (PE) in comparison to vitamin K antagonist (VKA) in routine clinical practice - RE-COVERY DVT/PE
Study reference number: 1160.188

Section 1: Milestones	Yes	No	N/A	Page Number(s)
1.1 Does the protocol specify timelines for				
1.1.1 Start of data collection 				15
1.1.2 End of data collection 				15
1.1.3 Study progress report(s)				
1.1.4 Interim progress report(s)				
1.1.5 Registration in the EU PAS register				15
1.1.6 Final report of study results				15

Comments:

Status reports will be generated on a regular basis and are dependent on recruitment, strategic decisions and regulatory requests, if applicable.

Section 2: Research question	Yes	No	N/A	Page Number(s)
2.1 Does the formulation of the research question and objectives clearly explain:				
2.1.1 Why the study is conducted? (e.g. to address an important public health concern, a risk identified in the risk management plan, an emerging safety issue)				18-19
2.1.2 The objectives of the study?				20
2.1.3 The target population? (i.e. population or subgroup to whom the study results are intended to be generalised)				21
2.1.4 Which formal hypothesis(-es) is (are) to be tested?				
2.1.5 If applicable, that there is no a priori hypothesis?				

Comments:

No formal hypothesis are being tested. The research questions, study objectives and analysis are defined in the protocol.

Section 3: Study design	Yes	No	N/A	Page Number(s)
3.1 Is the study design described? (e.g. cohort, case-control, randomised controlled trial, new or alternative design)				21

 Date from which information on the first study is first recorded in the study dataset or, in the case of secondary use of data, the date from which data extraction starts.

 Date from which the analytical dataset is completely available.

Section 3: Study design	Yes	No	N/A	Page Number(s)
3.2 Does the protocol specify the primary and secondary (if applicable) endpoint(s) to be investigated?				28-29
3.3 Does the protocol describe the measure(s) of effect? (e.g. relative risk, odds ratio, deaths per 1000 person-years, absolute risk, excess risk, incidence rate ratio, hazard ratio, number needed to harm (NNH) per year)				32-34

Comments:

--

Section 4: Source and study populations	Yes	No	N/A	Page Number(s)
4.1 Is the source population described?				21
4.2 Is the planned study population defined in terms of:				
4.2.1 Study time period?				15 & 21
4.2.2 Age and sex?				23
4.2.3 Country of origin?				2
4.2.4 Disease/indication?				23
4.2.5 Co-morbidity?				
4.2.6 Seasonality?				
4.3 Does the protocol define how the study population will be sampled from the source population? (e.g. event or inclusion/exclusion criteria)				23

Comments:

Patient recruitment is not restricted. Therefore co-morbidities are not part of the entry criteria. The planned recruitment period is over 2 years with no reference to seasonality.

Section 5: Exposure definition and measurement	Yes	No	N/A	Page Number(s)
5.1 Does the protocol describe how exposure is defined and measured? (e.g. operational details for defining and categorising exposure)				32
5.2 Does the protocol discuss the validity of exposure measurement? (e.g. precision, accuracy, prospective ascertainment, exposure information recorded before the outcome occurred, use of validation sub-study)				35
5.3 Is exposure classified according to time windows? (e.g. current user, former user, non-use)				35
5.4 Is exposure classified based on biological mechanism of action and taking into account the pharmacokinetics and pharmacodynamics of the drug?				
5.5 Does the protocol specify whether a dose-dependent or duration-dependent response is measured?				23

Comments:

No pharmacokinetic information will be collected in this study.

Section 6: Endpoint definition and measurement	Yes	No	N/A	Page Number(s)
6.1 Does the protocol describe how the endpoints are defined and measured?				30-32
6.2 Does the protocol discuss the validity of endpoint measurement? (e.g. precision, accuracy, sensitivity, specificity, positive predictive value, prospective or retrospective ascertainment, use of validation sub-study)				32-34

Comments:

--

Section 7: Confounders and effect modifiers	Yes	No	N/A	Page Number(s)
7.1 Does the protocol address known confounders? (e.g. collection of data on known confounders, methods of controlling for known confounders)				38-40
7.2 Does the protocol address known effect modifiers? (e.g. collection of data on known effect modifiers, anticipated direction of effect)				38-40

Comments:

--

Section 8: Data sources	Yes	No	N/A	Page Number(s)
8.1 Does the protocol describe the data source(s) used in the study for the ascertainment of:				
8.1.1 Exposure? (e.g. pharmacy dispensing, general practice prescribing, claims data, self-report, face-to-face interview, etc.)				32
8.1.2 Endpoints? (e.g. clinical records, laboratory markers or values, claims data, self report, patient interview including scales and questionnaires, vital statistics, etc.)				29-30
8.1.3 Covariates?				27-29
8.2 Does the protocol describe the information available from the data source(s) on:				
8.2.1 Exposure? (e.g. date of dispensing, drug quantity, dose, number of days of supply prescription, daily dosage, prescriber)				30
8.2.2 Endpoints? (e.g. date of occurrence, multiple event, severity measures related to event)				27-29
8.2.3 Covariates? (e.g. age, sex, clinical and drug use history, co-morbidity, co-medications, life style, etc.)				27-29
8.3 Is a coding system described for:				
8.3.1 Diseases? (e.g. International Classification of Diseases (ICD)-10)				
8.3.2 Endpoints? (e.g. Medical Dictionary for Regulatory Activities(MedDRA) for adverse events)				
8.3.3 Exposure? (e.g. WHO Drug Dictionary, Anatomical Therapeutic Chemical (ATC) Classification System)				
8.4 Is the linkage method between data sources described? (e.g. based on a unique identifier or other)				40

Comments:

Coding system will be described in detail in the data management plan.

Section 9: Study size and power	Yes	No	N/A	Page Number(s)
9.1 Is sample size and/or statistical power calculated?				31-33

Comments:

Section 10: Analysis plan	Yes	No	N/A	Page Number(s)
10.1 Does the plan include measurement of excess risks?				34-36
10.2 Is the choice of statistical techniques described?				34-36
10.3 Are descriptive analyses included?				34-36
10.4 Are stratified analyses included?				34-36
10.5 Does the plan describe the methods for adjusting for confounding?				34-36
10.6 Does the plan describe methods addressing effect modification?				34-36

Comments:

Additional information will be included in the SEAP.

Section 11: Data management and quality control	Yes	No	N/A	Page Number(s)
11.1 Is information provided on the management of missing data?				37
11.2 Does the protocol provide information on data storage? (e.g. software and IT environment, database maintenance and anti-fraud protection, archiving)				33
11.3 Are methods of quality assurance described?				37
11.4 Does the protocol describe possible quality issues related to the data source(s)?				37-39
11.5 Is there a system in place for independent review of study results?				

Comments:

There are no plans for an independent adjudication or data monitoring committee at time of protocol finalization.

Section 12: Limitations	Yes	No	N/A	Page Number(s)
12.1 Does the protocol discuss:				
12.1.1 Selection biases?				37-39
12.1.2 Information biases? (e.g. anticipated direction and magnitude of such biases, validation sub-study, use of validation and external data, analytical methods)				37-39

Section 12: Limitations	Yes	No	N/A	Page Number(s)
12.2 Does the protocol discuss study feasibility? (e.g. sample size, anticipated exposure, duration of follow-up in a cohort study, patient recruitment)				19-20
12.3 Does the protocol address other limitations?				37-39

Comments:

--

Section 13: Ethical issues	Yes	No	N/A	Page Number(s)
13.1 Have requirements of Ethics Committee/ Institutional Review Board approval been described?				39
13.2 Has any outcome of an ethical review procedure been addressed?				
13.3 Have data protection requirements been described?				39

Comments:

The protocol has not yet been submitted to an ethics review board.

Section 14: Amendments and deviations	Yes	No	N/A	Page Number(s)
14.1 Does the protocol include a section to document future amendments and deviations?				12

Comments:

--

Section 15: Plans for communication of study results	Yes	No	N/A	Page Number(s)
15.1 Are plans described for communicating study results (e.g. to regulatory authorities)?				46
15.2 Are plans described for disseminating study results externally, including publication?				

Comments:

Publication plan to be developed as a separate document.

Name of the main author of the protocol: \_\_\_\_\_

Date: dd/mm/year

Signature: \_\_\_\_\_

## **ANNEX 3. ADDITIONAL INFORMATION**

**ANNEX 3.1 MORISKY MEDICATION ADHERENCE SCALE**

©Morisky Medication Adherence Scale (MMAS-8-Item).		

You indicated that you are taking medication(s) for your Deep Venous Thrombosis (DVT) or Pulmonary Embolism (PE). Individuals have identified several issues regarding their medication-taking behavior and we are interested in your experiences. There is no right or wrong answer. Please answer each question based on your personal experience with your anticoagulation medication.
		
(Please check your answer below)		
	No=1	Yes=0
1. Do you sometimes forget to take your anticoagulation medication(s)?		
2. People sometimes miss taking their medications for reasons other than forgetting. Thinking over the past two weeks, were there any days when you did not take your anticoagulation medication(s)?		
3. Have you ever cut back or stopped taking your medication(s) without telling your doctor, because you felt worse when you took it?		
4. When you travel or leave home, do you sometimes forget to bring along your anticoagulation medication(s)?		
5. Did you take your anticoagulation medication(s) yesterday?		
6. When you feel like your anticoagulation is under control, do you sometimes stop taking your medication(s)?		
7. Taking medication(s) everyday is a real inconvenience for some people. Do you ever feel hassled about sticking to your [health concern] treatment plan?		

8. How often do you have difficulty remembering to take all your medication(s)?  
 (Please check your answer below)
- |                      |   |
|----------------------|---|
| Never/Rarely.....    | 4 |
| Once in a while..... | 3 |
| Sometimes.....       | 2 |
| Usually.....         | 1 |
| All the time.....    | 0 |

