### 9.3.1.3 Follow-up visit data points

The flowchart ([Table 9.3.1:2](#)) outlines all of the data points to be collected for patients who are followed.

- Type of data collection (i.e., based on routine clinic visit or telephone contact)
- Concomitant diseases (current, any changes)
- Available laboratory data that is associated with outcome events (e.g., CBC for major and clinically relevant non major bleeding events)
- INR for VKA patients
- Anticoagulation treatment (current, any changes (start or stop dates) including adherence, reasons for dose change). Adherence will be assessed using the Morisky Medication Adherence Scale (refer to the [Annex 3.1](#)).
- Changes in concomitant therapies
- Information on any outcome events that may have occurred since the previous visit. If the specific reversal agent for dabigatran is given, information surrounding the clinical circumstances, treatment, and clinical outcome will be collected on the CRF.
- Adverse drug reactions
- PACT-Q2 to be completed by the patient (collection of the PACT-Q2 should occur as close to the data collection time-point as possible). Refer to the [Annex 3.2](#).
- Details of health care resources utilization including:
  - Date, reason and duration of hospitalization occurring
  - Date and reason for visit to ER
  - Need to visit treating physician due to recurrent VTE event, bleeding event or for dose adjustment of anticoagulant therapy
  - For patients treated with VKA only:
    - The number of INR measurements and where the INR blood samples were drawn (e.g., physician's office, anticoagulation clinic, hospital, outpatient laboratory, self-monitoring)
    - At the 3 month data collection time-point *only*, the following details should be collected:
      - The distance traveled to have the INR measured
      - The time spent traveling to have the INR measured
      - If public transportation was used
    - If private transportation was used

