7.3 TREATMENT ADHERENCE AND PERSISTENCE

Treatment persistence will be assessed as time from treatment onset until permanent treatment discontinuation and summarized descriptively.

Time in therapeutic range (TTR) [3] calculated from INR results obtained at the respective timepoints will be analyzed. For each patient who took prescribed VKA, the TTR percentage will be calculated by linear interpolation between successive test results, and then the number of days in the therapeutic range will be estimated. For the target range 2.0 to 3.0 will be considered.

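### Annex 3.1 prints one response key (No=1, Yes=0) over items 1 to 7 of the adherence scale, which codes item 5 in the wrong direction

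*Protocol*

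**What the plan says.** Protocol Section 9.3.1.3 states: "Adherence will be assessed using the Morisky Medication Adherence Scale". Section 9.3.3 (Treatment adherence) names the same scale, and Table 9.3.1:2 schedules it at 3 months, 6 months and 1 year for Objective 2.

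Annex 3.1 is the only place in the two documents that shows codes for the scale:

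- **Items 1 to 7** share one pair of column headings, No=1 and Yes=0.
- **Item 5** is one of these seven and reads "Did you take your anticoagulation medication(s) yesterday".
- **Item 8**, on difficulty in remembering the medication, has its own codes, from 4 (never or rarely) down to 0 (all the time).

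The annex has no footnote or exception for item 5, no rule for adding up the items, and no statement of how item 8 enters a total.

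Section 7.3 of the Objective 2 SAP has adherence in its title, but the text covers only persistence and time in therapeutic range. On persistence it says: "Treatment persistence will be assessed as time from treatment onset until permanent treatment discontinuation and summarized descriptively". It does not mention the questionnaire.

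**The concern.** A scale score is interpretable only if all items point the same way. Under the printed key seven of the eight items do, and item 5 does not. A programmer working from the documents has no other key to follow and would build in one item with the wrong sign.

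What is at stake is the meaning of any reported adherence score: the most adherent pattern of answers would not earn the highest value. Protocol Section 9.9 (Recall bias) also relies on validated scales for adherence, and a wrongly coded item weakens that argument.

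**Working it through.** The plan states no total, maximum or cut-off for this scale, so there is no figure to reproduce. The check has two parts.

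**1. Direction of each item under the printed key (Annex 3.1).**

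| Item | Topic | Adherent answer | Printed code for that answer |
|---|---|---|---|
| 1 | sometimes forgets | No | 1 |
| 2 | missed days in the past two weeks | No | 1 |
| 3 | cut back or stopped without telling the doctor | No | 1 |
| 4 | forgets it when travelling | No | 1 |
| 5 | took it yesterday | Yes | 0 |
| 6 | stops when things feel under control | No | 1 |
| 7 | feels hassled by the plan | No | 1 |
| 8 | difficulty remembering | never or rarely | 4 (the highest) |

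Only item 5 gives its adherent answer the lower code. This part needs no assumption about how the items are combined.

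**2. Effect on a total, if the codes are summed.** The sum is an assumption. Let S = (codes of items 1 to 7) + (item 8). The reversed key differs only in coding item 5 as Yes=1, No=0.

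| Patient | Printed key | Item 5 reversed |
|---|---|---|
| Fully adherent | 6 + 0 + 4 = 10 | 6 + 1 + 4 = 11 |
| Same other answers, No to item 5 | 6 + 1 + 4 = 11 | 6 + 0 + 4 = 10 |
| Fully non-adherent | 0 + 1 + 0 = 1 | 0 + 0 + 0 = 0 |

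The gap between full adherence and full non-adherence is 10 − 1 = 9 points under the printed key and 11 − 0 = 11 under the reversed key.

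The result does not depend on the weight given to item 8. If item 8 is divided by 4 (also an assumption), the three totals are 7, 8 and 1 as printed, and 8, 7 and 0 with item 5 reversed.

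In general, let y = 1 if the patient took the drug yesterday and y = 0 if not. The printed code for item 5 is 1 − y and the reversed code is y. The error is (1 − y) − y = 1 − 2y, which is −1 for those who took it and +1 for those who did not. Every complete total is therefore off by exactly 1 point.

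The second row holds the other answers fixed. A patient who skipped yesterday would, if consistent, also answer Yes to item 2. That patient scores 5 + 1 + 4 = 10 under the printed key, which ties with the fully adherent patient. Under the reversed key the score is 5 + 0 + 4 = 9 against 11. In that case the printed key hides the missed dose instead of rewarding it.

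**Where the score is used.** Adherence is not among the Objective 2 outcomes in Protocol Section 9.3.2. It is not a covariate in SAP Table 7.6:1 (propensity model) or Table 7.6:2 (Cox model). The error has no route into the bleeding or VTE comparisons.

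**The case against.** The strongest reply is that Annex 3.1 is a copy of a patient form and not a scoring manual. The scale is a named, published instrument. The annex lists publications on it, and the protocol says only that adherence is assessed with it. The instrument's own scoring, or the sponsor's program, may already treat item 5 separately. SAP Sections 5.3, 6.4 and 7.7 are not in the public text, and a recoding rule could sit there. Item 7 still contains an unfilled placeholder, which suggests that the annexed copy may not be the form as fielded. All of this stands as a limit: the documents do not show that any score was or will be computed wrongly. It does not remove the point, because the one key the documents print is wrong for item 5 and nothing visible corrects it.

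A reader might infer three stronger things that the documents do not support:

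- **That the study's adherence score runs to 11 and is known to be wrong.** The maximum of 11 follows from summing the printed codes, which no document instructs.
- **That the dabigatran versus VKA comparison of adherence is biased.** No visible text specifies such a comparison. If one were made on summed scores, the error in the group difference would be −2 × (p_DE − p_VKA), where p is the proportion that took the drug yesterday. It is zero if the two proportions are equal, and the documents give neither.
- **That mean adherence is understated by a known amount.** The mean error is 1 − 2p. It is −0.8 at p = 0.90 and −0.9 at p = 0.95, but those proportions are assumptions with no source in the documents.

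**Conclusion.** The point holds as an error in the printed response key. Item 5 is coded against the direction of the other seven items, and no visible text reverses it. If the codes are summed, a patient who took yesterday's dose scores 1 point lower than one with the same other answers who did not, and each complete total differs by 1 point from the correctly directed one. The direction error itself rests on no assumption; the 1-point size rests on the sum rule, which the documents do not state.

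The consequence is minor. It is confined to the adherence measure at 3, 6 and 12 months. The sample size, the primary safety and effectiveness outcomes, and the propensity-score and Cox analyses are untouched. Whether a reported result is affected depends on the scoring program, which the documents do not show.

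**What to change.** In Annex 3.1, or in Section 7.3 of the Objective 2 SAP, state that item 5 is coded Yes=1, No=0. In the same place, say whether the items are summed and how item 8 (0 to 4) enters. Check that the scoring program follows this rule before any adherence result is reported. If the program already reverses item 5, a note recording that is enough.

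The cost is one line of text and, at most, one line of code. The raw Yes and No answers remain valid, so no data are lost and no patient needs to be contacted again.
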